11.2.3 Expedited reporting of adverse events to DAIDS

Requirements, definitions and methods for expedited reporting of AEs are outlined in Version 2.0 (January 2010) of the *Manual for Expedited Reporting of Adverse Events* to DAIDS (DAIDS EAE Manual), which is available on the RSC website at http://rsc.tech-res.com/clinical-research-sites/safety-reporting. The SAE Reporting Category will be used for this study.

The internet-based DAIDS Adverse Experience Reporting System (DAERS) must be used for expedited AE reporting to DAIDS. In the event of system outages or technical difficulties, expedited AE reports may be submitted via the DAIDS EAE Form. For questions about DAERS, please contact [contact] or from within the DAERS application itself.

For questions about expedited AE reporting, please contact the RSC ([contact]).

The study products for which expedited reporting are required are:

- p24CE1/2 pDNA or placebo
- p55^{gag} pDNA or placebo
- *IL-12* pDNA or placebo
- Intramuscular TriGrid Delivery System (TDS-IM) electroporation device

While the participant is in the main study reporting period (See Section 3), the SAE Reporting Category will be used.

If the participant has completed the main study (visit 13, Month 12) and is in the "followup health contact" reporting period (see Section 3) the SUSAR Reporting Category will be used (In addition, please note, per Section 9.5, all adverse events that are serious are collected on the month 18 Health Contact Event Log and reported to SCHARP.)

After the participant has completed the month 18 health contact and is off study, sites must report SUSARS if the study site staff becomes aware of the events on a passive basis (eg, from publicly available information)

The NIAID/DAIDS will report all unexpected SAEs related to the study products observed in this clinical trial to the FDA in accordance with 21 CFR 312.32 (IND Safety Reports). However, because safety is a primary study endpoint, the Sponsor Medical Officer will not routinely be unblinded to study treatment assignment when there is an assessment of relatedness of the SAE with the study product(s); and the safety report will be sent to the FDA based on the blinded attribution assessment.

If the PSRT believes unblinding of the site PI to treatment assignment will assist with the clinical management of the SAE, the PSRT will consult the independent HVTN SMB for a recommendation. In the event the HVTN SMB determines that unblinding is indicated, the SMB will inform the site physician of the participant's treatment assignment in such a manner as to maintain the study blind of the PSRT and study team. For additional impact and management of SAEs on the study, refer to Section 11.4.

11.3 Safety reviews

11.3.1 Initial safety evaluation

Enrollment across all participating HVTN CRSs will be restricted to a maximum of 1 participant per day and restricted to US sites until 10 participants have been enrolled. The HVTN 119 PSRT will review the cumulative safety data including at minimum local and systemic reactogenicity data reported for the first 72 hours postvaccination on each of

these 10 participants, and will determine whether it is safe to proceed with full enrollment.

11.4 Safety pause and prompt PSRT AE review

When a trial is placed on safety pause, all enrollment and vaccinations will be held until further notice. The AEs that will lead to a safety pause or prompt HVTN 119 PSRT AE review are summarized in Table 11-1. Vaccinations may be suspended for safety concerns other than those described in the table, or before pause rules are met, if, in the judgment of the HVTN 119 PSRT, participant safety may be threatened. Criteria for an individual participant's departure from the schedule of vaccinations are listed in Section 7.3.

Event and relationship to study			
products	Severity	HVTN CRS action ^a	HVTN Core action
SAE, related	Grade 5 or Grade 4	Phone immediately, email and submit forms immediately	Immediate pause
SAE, not related	Grade 5	Phone immediately, email and submit forms immediately	Immediate HVTN 119 PSRT notification
SAE, related	Grade 3	Email and submit forms immediately	Prompt HVTN 119 PSRT AE review to consider pause
AE ^b , related	Grade 4 or 3	Email and submit forms immediately	Prompt HVTN 119 PSRT AE review to consider pause

Table 11-1 AE notification and safety pause/AE review rules

^a Phone numbers and email addresses are found on the Protocol home page on the HVTN Members' site

(https://members.hvtn.org/protocols/hvtn119).

^b Does not include subjective reactogenicity symptoms (injection site pain, tenderness, fatigue/malaise, myalgia, arthralgia, chills, headache, nausea).

For all safety pauses, HVTN Core notifies the HVTN 119 PSRT, HVTN Regulatory Affairs, DAIDS Pharmaceutical Affairs Branch (PAB), DAIDS Regulatory Affairs Branch (RAB), DAIDS Safety and Pharmacovigilance Team (SPT), and participating HVTN CRSs. When an immediate safety pause is triggered, HVTN Core notifies the SMB.

Once a trial is paused, the HVTN 119 PSRT reviews safety data and decides whether the pause can be lifted or permanent discontinuation of vaccination is appropriate, consulting the SMB if necessary. HVTN Core notifies the participating HVTN CRSs, HVTN Regulatory Affairs, DAIDS PAB, DAIDS RAB, and DAIDS SPT of the decision regarding resumption or discontinuation of study vaccinations. Based on the HVTN 119 PSRT assessment, DAIDS RAB notifies the FDA as needed.

If an immediate HVTN 119 PSRT notification or prompt HVTN 119 PSRT AE review is triggered, HVTN Core notifies the HVTN 119 PSRT as soon as possible during working hours (US Pacific Time)—or, if the information was received during off hours, by the morning of the next work day. If a prompt HVTN 119 PSRT AE review cannot be

completed within 72 hours of notification (excluding weekends and US federal holidays), an automatic safety pause occurs.

The HVTN requires that each CRS submit to its IRB/EC and any applicable RE protocolrelated safety information (such as IND safety reports, notification of vaccine holds due to the pause rules, and notification of other unplanned safety pauses). CRSs must also follow all applicable RE reporting requirements.

In addition, all other AEs are reviewed routinely by the HVTN 119 PSRT (see Section 11.5.2).

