7.3.3 Discontinuing vaccination for a participant

Under certain circumstances, an individual participant's vaccinations will be permanently discontinued. Specific events that will result in stopping a participant's vaccination schedule include:

- Co-enrollment in a study with an investigational research agent (rare exceptions allowing for the continuation of vaccinations may be granted with the unanimous consent of the HVTN PSRT).
- Clinically significant condition (ie, a condition that affects the immune system or for which continued vaccinations and/or blood draws may pose additional risk), including but not limited to the following:
 - Pregnancy (regardless of outcome);
 - Any grade 4 local or systemic reactogenicity symptom, lab abnormality, or AE that is subsequently considered to be related to study products.
 - Any grade 3 lab abnormality or other clinical AE (exception: fever or vomiting and subjective local and systemic symptoms) that is subsequently considered to be related to study products; or
 - Clinically significant type 1 hypersensitivity reaction associated with study vaccination. Consultation with the HVTN PSRT is required prior to subsequent vaccinations following any type 1 hypersensitivity reaction associated with study vaccination; or
- Investigator determination in consultation with Protocol Team leadership (eg, for repeated nonadherence to study staff instructions).

Such participants should be counseled on the importance of continuing with the study and strongly encouraged to participate in follow-up visits and protocol-related procedures per the protocol for the remainder of the trial, unless medically contraindicated.

In addition, vaccinations will be stopped for participants diagnosed with HIV infection. HIV-infected participants will not continue in the trial (see Section 7.3.4).

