11.1.3 SDMC roles and responsibilities in safety monitoring

The roles and responsibilities of the SDMC in relation to safety monitoring include:

• Maintaining a central database management system for HVTN clinical data;

• Providing reports of clinical data to appropriate groups such as the HVTN 119 PSRT and HVTN SMB (see Section 11.1.2);

11.1.4 **HVTN** Core roles and responsibilities in safety monitoring

- Daily monitoring of clinical data for events that meet the safety pause and HVTN 119 PSRT AE review criteria (see Section 11.4);
- Notifying HVTN CRSs and other groups when safety pauses or planned holds are instituted and lifted (see Section 11.4);
- Querying HVTN CRSs for additional information regarding reported clinical data; and
- Providing support to the HVTN 119 PSRT.

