11.5.1 Daily review

Blinded daily safety reviews are routinely conducted by HVTN Core for events requiring expedited reporting to DAIDS, and events that meet safety pause criteria or prompt HVTN 119 PSRT AE review criteria.

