11.5.2 Weekly review

During the injection phase of the trial, the HVTN 119 PSRT reviews clinical safety reports on a weekly basis and conducts calls to review the data as appropriate. After the injections and the final 2-week safety visits are completed, less frequent reporting and safety reviews may be conducted at the discretion of the HVTN 119 PSRT. HVTN Core reviews reports of clinical and laboratory AEs. Events identified during the review that are considered questionable, inconsistent, or unexplained are referred to the HVTN CRS clinic coordinator for verification.

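### Table 11-1 exempts subjective reactogenicity symptoms from prompt safety review even at grade 4, the level at which the participant's own vaccinations stop

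*Protocol*

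**What the plan says.** **Trial-level rule.** Table 11-1 in Protocol Section 11.4 puts related AEs of grade 4 and grade 3 in one row. The site must email and submit forms immediately, and the PSRT reviews promptly to consider a pause. Footnote b is attached to the AE entry of that row and so applies to both grades: "Does not include subjective reactogenicity symptoms (injection site pain, tenderness, fatigue/malaise, myalgia, arthralgia, chills, headache, nausea".

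**Individual rule.** Section 7.3.3 permanently stops vaccination for "Any grade 4 local or systemic reactogenicity symptom, lab abnormality, or AE that is subsequently considered to be related to study products". The next bullet, at grade 3, carries an exception: "Any grade 3 lab abnormality or other clinical AE (exception: fever or vomiting and subjective local and systemic symptoms". The exception is absent at grade 4.

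**What depends on Table 11-1.** Core's duty in Section 11.1.4 is "Daily monitoring of clinical data for events that meet the safety pause and HVTN 119 PSRT AE review criteria". Section 11.5.1 limits the daily review to events needing expedited reporting and "events that meet safety pause criteria or prompt HVTN 119 PSRT AE review criteria". If a triggered prompt review is not "completed within 72 hours of notification (excluding weekends and US federal holidays), an automatic safety pause occurs".

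**The default route.** For everything else Section 11.4 says: "In addition, all other AEs are reviewed routinely by the HVTN 119 PSRT (see Section 11.5.2". Section 11.5.2 reads: "During the injection phase of the trial, the HVTN 119 PSRT reviews clinical safety reports on a weekly basis", with calls as appropriate. It sets no deadline for a decision and provides no automatic pause.

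**The concern.** Section 7.3.3 treats grade 4 as different in kind: a subjective symptom that is tolerated at grade 3 ends that person's dosing at grade 4. Table 11-1 makes no such distinction for the eight listed symptoms.

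A grade 3 exemption is easy to understand. Section 4.5 says electroporation causes considerably more acute discomfort than an ordinary injection, and Table 4-4 lists severe injection site pain or tenderness as a known risk. The documents give no reason to extend the exemption to grade 4.

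At stake is whether other participants go on being dosed while nobody is required to decide. This is the first human use of p24CE1/2 (Section 4.10.1). The total IL-12 pDNA dose of 2 mg is above the earlier maximum of 1.5 mg in HVTN studies with electroporation (Section 4.6.1).

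**Working it through.** The plan gives no figure to reproduce. The check traces one event through the rules and then sizes the delay.

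**1. Rule trace: a related, non-serious, grade 4 symptom from the footnote b list**

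| Rule | Applies? | Reason |
|---|---|---|
| Immediate pause (Table 11-1, row 1) | No | Needs an SAE |
| Immediate email and forms; prompt PSRT review (row 4) | No | Footnote b |
| Automatic pause at 72 hours (11.4) | No | Needs a triggered prompt review |
| Expedited report to DAIDS (11.2.3) | No | SAE reporting category |
| Required daily Core review (11.1.4, 11.5.1) | No | Not an expedited, pause or prompt-review event |
| Forms by end of next business day (11.2.1) | Yes | All safety forms |
| Weekly PSRT review (11.4, 11.5.2) | Yes | Default route |
| Participant's own vaccinations stop (7.3.3) | Yes | No exception at grade 4 |

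The general statement on daily monitoring in Section 2.5 does not change this, because Sections 11.1.4 and 11.5.1 define its scope.

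**2. Time to the limit of each route, from when the site learns of the event**

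Assumptions: no federal holiday; working day 09:00 to 17:00; forms sent at their deadline; reports every 7 days, reviewed the same day.

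- Prompt limit, Monday 09:00 event: to Thursday 09:00 = 3.0 days.
- Prompt limit, Friday 18:00 event: PSRT notified Monday 09:00 (2.625 days), plus 3 days = 5.625 days.
- Forms deadline, Monday 09:00 event: to Tuesday 17:00 = 32/24 = 1.33 days.
- Forms deadline, Friday 18:00 event: to Monday 17:00 = 71/24 = 2.96 days.
- Weekly route = forms deadline + wait for the next report.
- Gap = weekly route − prompt limit.

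| Wait for report | Monday: weekly route | Gap | Friday: weekly route | Gap |
|---|---|---|---|---|
| 0 days (best) | 1.33 | −1.67 | 2.96 | −2.67 |
| 3.5 days (average) | 4.83 | +1.83 | 6.46 | +0.83 |
| 7 days (worst) | 8.33 | +5.33 | 9.96 | +4.33 |

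A negative gap means the weekly review comes before the prompt limit would have expired.

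**3. Vaccination visits in the gap**

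Inputs from Section 3: 56 participants, 4 vaccination visits each, 26 months in total, 18 months per participant. Even accrual is assumed.

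- Accrual: 26 − 18 = 8 months; 56/8 = 7 participants a month.
- Mean rate: 56 × 4 = 224 visits over 8 + 6 = 14 months = 16 a month, or 3.7 a week.
- Peak rate, with all four visits overlapping: 4 × 7 = 28 a month, or 6.4 a week.
- Further visits = gap/7 × weekly rate.
- Average wait: 0.83/7 × 3.7 = 0.4, up to 1.83/7 × 6.4 = 1.7.
- Worst case: 4.33/7 × 3.7 = 2.3, up to 5.33/7 × 6.4 = 4.9.

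**The case against.** Four arguments deserve an answer.

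**Section 7.3.3 need not be the benchmark.** Individual stopping and trial-level review serve different purposes, and the two rules already differ elsewhere. Related grade 3 fever and vomiting are exempt from individual stopping, yet footnote b does not list them, so they still get prompt review. That is correct, and the rules do not conflict. But there the trial-level rule is the stricter one. Among graded related events at grade 3 or 4, the eight listed symptoms at grade 4 are the only place where it is weaker than the individual rule.

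**The event may hardly exist.** A grade 4 symptom that is serious triggers an immediate pause, which is stronger than the fix proposed here. The symptom grading criteria and the SAE definition are in external manuals. Table 11-1 has a separate row for related non-serious grade 4 AEs, so the protocol foresees such events, but laboratory abnormalities alone could explain that row. This stands in part: the share of grade 4 subjective symptoms that would be non-serious is unknown.

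**Other safeguards cover it.** A clinician generally sees any reaction greater than mild within 48 hours (Section 9.9). Forms arrive by the end of the next business day. Sites can call the safety phone or notify the clinical safety specialist (Section 11.2.2), who sits on the PSRT. The PSRT can hold calls or suspend dosing on its own judgment, and it reviews the first 10 participants (Section 11.3.1). All of this is real. But the duty to notify the specialist concerns serious safety concerns and points back to Table 11-1, and suspension is discretionary. The first-10 review needs only 72 hours of postvaccination data, while Group 1 first receives the three-plasmid mixture at Month 3.

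**The dose evidence is reassuring.** IL-12 pDNA at 1 mg per site was well tolerated before (Section 4.6.1), and another IL-12 plasmid was given into tumors at up to 5.8 mg without dose-limiting systemic toxicity (Section 4.10.3). This supports a low expected frequency.

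**Conclusion.** The concern holds. No rule requires a prompt PSRT decision on a related, non-serious grade 4 event among the eight symptoms once the first-10 evaluation is over. The event is not unreviewed; what is missing is the deadline.

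The practical size is small. The delay ranges from none to just over 5 days, and dosing may continue during a prompt review too, unless the PSRT acts. The visit counts apply only if an event occurs, and they matter only if the PSRT would have suspended dosing. They also rest on a fixed weekly cycle, forms sent at their deadline, even accrual and no PSRT action between reports. No endpoint, estimate or sample size is affected. The change is still worth making, because in a first-in-human trial a grade 4 related reaction should lead to a decision about other participants by a set time. Confidence is medium, since the number of affected events cannot be determined from the documents.

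**What to change.** Insert the words Grade 3 in footnote b of Table 11-1, so that only grade 3 events among the eight listed symptoms are exempt. Related grade 4 events among them then fall under row 4: immediate notification, daily Core review and prompt PSRT review with the 72-hour limit. Leave Section 7.3.3 and the other rows unchanged. A letter of amendment, one of the routes named in Section 13, is enough.

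The cost is a few extra prompt reviews. If one runs late, the automatic pause holds all enrollment and vaccination, and a dose whose window passes cannot be given (Section 7.3.2). That could leave fewer complete vaccine series in a comparison planned on 21 evaluable participants per arm (Section 6.1.2). The risk is small and arises only if the PSRT misses its own limit.

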11.5 Review of cumulative safety data

Routine safety review occurs at the start of enrollment and then throughout the study.

Reviews proceed from a standardized set of protocol-specific safety data reports. These reports are produced by the SDMC and include queries to the HVTN CRSs. Events are tracked by internal reports until resolution.

11.5.1 Daily review

Blinded daily safety reviews are routinely conducted by HVTN Core for events requiring expedited reporting to DAIDS, and events that meet safety pause criteria or prompt HVTN 119 PSRT AE review criteria.

11.5.2 Weekly review

During the injection phase of the trial, the HVTN 119 PSRT reviews clinical safety reports on a weekly basis and conducts calls to review the data as appropriate. After the injections and the final 2-week safety visits are completed, less frequent reporting and safety reviews may be conducted at the discretion of the HVTN 119 PSRT. HVTN Core reviews reports of clinical and laboratory AEs. Events identified during the review that are considered questionable, inconsistent, or unexplained are referred to the HVTN CRS clinic coordinator for verification.

11.6 Study termination

This study may be terminated early by the determination of the HVTN 119 PSRT, a pertinent national regulatory authority, NIH, Office for Human Research Protections (OHRP), FDA, or vaccine developer(s). In addition, the conduct of this study at an individual HVTN CRS may be terminated by the determination of the IRB/EC and any applicable RE.

12 Protocol conduct

This protocol and all actions and activities connected with it will be conducted in compliance with the principles of GCP (ICHe6), and according to DAIDS and HVTN policies and procedures as specified in the *HVTN Manual of Operations*, DAIDS Clinical Research Policies and Standard Procedures Documents including procedures for the following:

- Protocol registration, activation, and implementation;
- Informed consent, screening, and enrollment;
- Study participant reimbursement;
- Clinical and safety assessments;
- Safety monitoring and reporting;
- Data collection, documentation, transfer, and storage;
- Participant confidentiality;
- Study follow-up and close-out;
- Unblinding of staff and participants;
- Quality control;
- Protocol monitoring and compliance;
- Advocacy and assistance to participants regarding negative social impacts associated with the vaccine trial;
- Risk reduction counseling;
- Specimen collection, processing, and analysis;
- Ancillary studies, and
- Destruction of specimens.

Any policies or procedures that vary from DAIDS and HVTN standards or require additional instructions (eg, instructions for randomization specific to this study) will be described in the *HVTN 119 Study Specific Procedures*.

12.1 Social impacts

Participants in this study risk experiencing discrimination or other personal problems, resulting from the study participation itself or from the development of VISP. The HVTN CRS is obliged to provide advocacy for and assistance to participants regarding these negative social impacts associated with the vaccine trial. If HVTN CRS staff have questions regarding ways to assist a participant dealing with a social impact, a designated NIAID or HVTN Core representative can be contacted.

Social harms are tabulated by the SDMC and are subjected to descriptive analysis. The goal is to reduce their incidence and enhance the ability of study staff to mitigate them when possible.

Summary tables of social impact events will be generated weekly, and made available for review by the protocol chairs, protocol team leader, and the designated NIAID representative.

12.2 Compliance with NIH guidelines for research involving products containing recombinant or synthetic Nucleic Acid Molecules

Because this study is evaluating products containing recombinant or synthetic DNA, it must comply with regulations set forth in the *NIH Guidelines for Research Involving Recombinant or Synthetic Nucleic Acid Molecules (April 2016)*. Information about the study must be submitted to site Institutional Biosafety Committees (IBCs) and Institutional Review Boards/Ethics Committees (IRBs/ECs). IBCs and IRBs/ECs must provide a written assessment of whether Recombinant DNA Advisory Committee (RAC) review is warranted. In exceptional cases that meet specific criteria outlined in the *NIH Guidelines Appendix M-I-B*, IBCs and IRBs/ECs assessment can include a request for RAC review. Regardless of the potential for RAC review, the HVTN and DAIDS will register the protocol with the NIH Office of Scientific Policy (OSP). The Protocol Team, jointly with Profectus BioSciences, Inc., will prepare the NIH OSP registration documents.

Investigators at each site are responsible for obtaining IBC approval per NIH Guidelines *section IV-B7-a-(1)*. IBC review and approval must be documented by the investigator and submitted as part of DAIDS's initial protocol registration for this trial before participants are enrolled at the site. If this protocol is amended, investigators should follow the requirements of their IBC.

The HVTN and DAIDS will ensure that reporting requirements to NIH OSP, as outlined in *Appendix M-I-C-1.Initiation of the Clinical Investigation, Appendix M-I-C-*2.Additional Clinical Trial Sites. Appendix M-I-C-3.Annual Reports and Appendix M-I-C-4.Safety Reporting are satisfied per the NIH Guidelines.

